### 9.3 Statistical Methods

Baseline characteristics will be summarized as means with standard deviations or proportions, as appropriate. In the primary analysis we will quantify the treatment effect of a strategy aimed at risk factor modification by intensive blood pressure treatment, monitoring with a blood pressure measuring device, and acetylsalicylic acid (ASA) on the risk of aneurysm rupture or growth, which is an established surrogate for the risk of rupture, compared with standard blood pressure treatment and no ASA.

We will compare the occurrence of outcome events in the two groups in terms of the risk ratio (RR), which will be obtained by means of a Poisson model. The precision of the RR estimates will be described with 95% confidence intervals obtained from the Poisson model. Our primary analyses will be based on the intention-to-treat principle. Patients will be censored in case of death from causes other than aneurysm rupture. In addition to crude analyses, we will do an analysis adjusted for the main risk factors of the primary outcome: aneurysm size, shape, location, age and smoking status. For our secondary analyses in which the timing of the outcome event is not prespecified but all follow-up data are taken into account, we will calculate hazard ratios using Cox regression analyses. Final details will be specified in the Statistical Analysis Plan.

We plan the following subgroup analyses: age ( $\leq 55$  versus  $> 55$  years), sex, and type (with or without previous rupture of another aneurysm), size (1.0-4.0 mm versus  $\geq 4.1$  mm), aneurysm location (posterior communicating artery / anterior communicating artery / posterior circulation versus all other aneurysms) and morphology of aneurysm (regular versus irregular shape).

In addition to our main research question on the effect of combined ASA and blood pressure lowering therapy, a secondary aim is to study the effect of the blood pressure component of the combination therapy. For this aim we will accurately record who is using intensive blood pressure lowering therapy. Data of both the intervention and the control arms of PROTECT-U can be used for this purpose. For this research aim we will relate the intensive blood pressure lowering therapy usage percentage to the primary outcome. As this analysis pertains to a non-randomized comparison we need to adjust for potential confounding by other determinants of the primary outcome, including the other component (acetylsalicylic acid) of the combined treatment. Analyses will be done with multivariable Poisson regression in which we will model cumulative incidence of the primary outcome at three years.

We will do an additional analysis restricted to the patients randomized to the intervention group, because within this group detailed data on achieved blood pressure will be available obtained with a device that transmits blood pressure to a central post. For each patient we will calculate the percentage of time that systolic blood pressure is below 120 mm Hg. Then we will do an

analysis similar as described above in which we will relate the percentage of time that systolic blood pressure is below 120 mm Hg to the primary outcome, also adjusted for other determinants of the outcome.

Another secondary aim is to study the effect of ASA treatment alone. For these analyses, we will use data on drug accountability (for acetylsalicylic acid use). As these analyses pertain to non-randomized comparisons, we need to adjust for potential confounding by other determinants of the primary outcome, including the other component of the combined treatment. Analyses will be done with multivariable Poisson regression in which we will model cumulative incidence of the primary outcome at three years. These data will not be subject to an interim analysis.

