## 5.5 Randomisation

### 5.5.1 Randomisation method

For randomisation an online tool (<https://www.randomizer.at/>) will be used. Any patient included will be 1:1 randomised into one of the two study arms: 1) a strategy with ASA 81 - 100mg/day and intensive blood pressure treatment (targeted systolic blood pressure below 120mmHg) with weekly measurements using a home blood pressure measuring device; or 2) standard of care.

There is no placebo group. Each study centre will be provided with an access code to perform the randomisation independently. Stratification will occur according to centre.

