## 9 STATISTICAL PROCEDURES

### 9.1 Sample Size Calculation

The test of the primary hypothesis is outlined in paragraph 9.4 (Statistical Methods). The sample size calculation is based on the following assumptions:

Previously a hazard ratio of 1.3 (95%CI 1.0-1.9) for hypertension as a risk factor for aneurysm rupture (PHASES cohort) and an odds ratio of 0.27 (95% CI 0.27-0.67) for risk of rupture in patients with unruptured intracranial aneurysms using ASA was reported. If we conservatively assume a risk reduction of 45% for the primary outcome measure and the risk to have a primary outcome event at three years of 15% in the standard treatment group and 8.25% in the intensive treatment + ASA group, an alpha of 0.05 and a power of 80%, 353 patients are needed in each group. Assuming a dropout rate of 10%, we will need to assign 776 patients to the trial so that 706 patients can be analyzed.

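### The 95% interval for the primary risk ratio is taken from a Poisson model with no robust variance named; read literally it is about 6% too wide on the log scale and does not match the binomial sample size.

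*Protocol*

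**What the plan says.** Sections 2.1, 7.2 and 9.1 define the primary outcome as rupture or growth within a fixed window of 36±6 months, which is one yes/no result per patient. Section 9.3 compares the arms by a risk ratio from a Poisson model and says where the interval comes from: "The precision of the RR estimates will be described with 95% confidence intervals obtained from the Poisson model". The synopsis says the same. Neither place mentions a robust or sandwich variance.

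Section 9.3 also plans covariate adjustment: "In addition to crude analyses, we will do an analysis adjusted for the main risk factors of the primary outcome". The factors listed are aneurysm size, shape, location, age and smoking. Centre is not among them, although section 5.5.1 says: "Stratification will occur according to centre".

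The sample size in section 9.1 reads: "an alpha of 0.05 and a power of 80%, 353 patients are needed in each group". Section 9.1 refers the reader to the statistical methods for the test of the primary hypothesis, but no test is named there. Section 9.3 leaves final details to the statistical analysis plan, which is not at hand.

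**The concern.** A Poisson model gives the correct risk ratio for a yes/no outcome, but its own standard errors treat the variance of each result as p. The true variance is p(1-p), so the model-based standard error is too large, and increasingly so as the risk rises. At risks near 15% the excess is not trivial.

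Two things are at stake. The reported interval would be wider than the data warrant. And if the conclusion is read from whether that interval excludes 1, the trial has less power than its sample size was meant to buy. Recruitment is planned from 2017 to 2026, and section 3.1 rejects larger designs as unfeasible, so precision lost through a variance formula is worth recovering.

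**Working it through.** **Inputs, all from section 9.1.** Control risk: "the risk to have a primary outcome event at three years of 15% in the standard treatment group". Intervention risk: "8.25% in the intensive treatment + ASA group". This gives a risk ratio of 0.55. Alpha is 0.05, power 80%, and 353 patients are analysed per arm. Sidedness is not stated; two-sided reproduces the figure (one-sided would give 278).

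**Step 1: reproduce the protocol's figure.** Two-proportion formula, pooled variance under the null, two-sided, no continuity correction, mean risk 0.11625:

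n = [1.960 × √(2 × 0.11625 × 0.88375) + 0.842 × √(0.15 × 0.85 + 0.0825 × 0.9175)]² / 0.0675² = 352.8, rounded up to 353.

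The 353 therefore rests on binomial variance.

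**Step 2: standard error of the log risk ratio.** Expected events are 353 × 0.15 = 52.95 and 353 × 0.0825 = 29.12.

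- Poisson, model-based: √(1/52.95 + 1/29.12) = 0.2307
- Binomial or robust: √(0.85/52.95 + 0.9175/29.12) = 0.2181

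The ratio is 1.058 and the variance ratio is 1.119. As an equivalence only (no patient is lost), 706 − 706/1.119 is about 75 patients' worth of information.

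**Step 3: the interval at a risk ratio of 0.55,** exp(ln 0.55 ± 1.96 × SE).

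- Poisson: 0.35 to 0.86
- Robust: 0.36 to 0.84

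Coverage of the Poisson interval at the design effect is about 96.2%.

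**Step 4: power and type I error if significance means that the interval excludes 1.** Exact enumeration of the two binomials:

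| | Poisson, model-based | Robust |
|---|---|---|
| Power, 353 per arm | 76.4% | 80.1% |
| Power, 349 per arm (776 less 10%) | 75.9% | 79.6% |
| Type I error, 15% in both arms | 3.2% | 4.8% |
| Type I error, 11.625% in both arms | 3.5% | 4.8% |

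The normal approximation gives lower power for both (74.8% and 78.3% at 353 per arm) with a similar gap. Keeping 80% with the model-based interval would take about 385 analysed patients per arm by exact enumeration, or 400 by normal approximation.

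The two intervals can also disagree on one data set. With 53 versus 35 events among 353 per arm, the Poisson upper limit is 1.01 (p = 0.057) and the robust upper limit is 0.99 (p = 0.042).

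**Step 5: what centre contributes.** The protocol does not say how much risk varies between centres, so a spread has to be assumed. Simulation with 30 centres, arms balanced within centre, and a between-centre standard deviation (SD) on the logit scale of 0 to 1.0:

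| Assumed SD | Unstratified Poisson, power | Unstratified robust, power | Mantel-Haenszel by centre, power |
|---|---|---|---|
| 0 | 76.6% | 80.3% | 80.3% |
| 0.5 | 76.4% | 80.2% | 80.7% |
| 1.0 | 76.8% | 80.6% | 82.6% |

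At an SD of 1.0 the unstratified robust interval has type I error 3.0%, against 4.8% when stratified. In one simulated data set, adding centre to the Poisson model left the model-based standard error at 0.2599. Only the robust one moved, from 0.2479 to 0.2449.

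**The case against.** **The variance estimator may only be unstated.** A sandwich interval is also obtained from a Poisson model, and section 9.3 defers final details to the analysis plan. This lowers confidence that the wrong interval would be used. But the protocol does say where the interval comes from, and the plain reading is the model-based one.

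**No test is named.** This stands. Power of 76.4% and type I error of 3.2% belong to a decision read from the interval. A separate chi-square test, matching the sample-size formula, would have exact power of 80.7% at 353 per arm. The width of the interval does not depend on this point.

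**The model might use person-time.** Section 9.3 censors patients at death from other causes, which suggests follow-up time. With a person-time offset the Poisson variance is appropriate: with constant hazards and exact event times, power is about 80% and type I error 4.9%. But no offset is mentioned, it would yield a rate ratio where the protocol states a risk ratio, and section 9.3 reserves Cox regression for analyses without a prespecified time.

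**Stronger readings that a reader might infer.** One is that leaving out centre causes the wide interval. Step 5 does not support this: nearly all of the loss comes from the variance, and centre matters visibly only under a large assumed spread. Another is that the five-factor adjusted model has to be primary. That is a preference, since the protocol already plans this analysis. With about 82 expected events over roughly 30 sites (under 3 per site), a model with every centre and five factors would be sparse. A third is that the result could be falsely positive; the error runs the other way.

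**Conclusion.** The point holds for the variance. Read literally, section 9.3 gives an interval whose log-scale width is 5.8% too large at the design values, and it does not match the binomial variance behind the 353 per group. If the interval also decides significance, exact power falls from 80.1% to 76.4%.

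This rests on three readings: a binary outcome without a person-time offset, a model-based variance, and, for power and type I error only, a decision made from the interval. The first two are the plain sense of the text, but the unseen analysis plan could settle the second differently. The loss is conservative and moderate, so this is a clarification well worth making and not a flaw that undermines the trial. Accounting for centre is good practice after stratified randomisation, with a small expected gain.

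**What to change.** In section 9.3, the synopsis and the analysis plan, state that the primary risk ratio and its 95% interval come from Poisson regression with a robust (sandwich) variance, or from another risk-ratio method with binomial variance, and that the primary test is based on the same method. This restores about 80% power at 353 per arm.

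State also how centre is accounted for, in a way that tolerates sparse sites: for example a Mantel-Haenszel risk ratio stratified by centre, or small centres pooled by a rule fixed in advance. Adding centre without a robust or binomial variance would not recover the power. The crude and adjusted analyses can otherwise stay as planned.

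The cost is a few sentences, with no new data and no extra patients. It should be settled before outcomes are compared by arm, because the two intervals can differ on whether 1 is excluded.

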## 6.2 Baseline Visit

The following are key elements of the baseline visit:

- Confirmation that all inclusion- / exclusion criteria are satisfied
- If a recent (<6 months) GFR (determined at the lab of the trial center or at another lab that provides a copy of the appropriate lab certificate) is not available, a blood test will be done to measure GFR after informed consent has been obtained.
- Verification of participant contact information
- Completion of the study randomization procedure using an online randomization tool, as soon as lab values needed for inclusion (e.g. negative pregnancy testing) are available.
- Collection of the following baseline characteristics by history taking: history of hypertension / ischemic stroke / intracerebral hemorrhage / subarachnoid hemorrhage / myocardial infarction / peripheral vascular disease / polycystic kidney disease, tobacco smoking history including number of packyears of smoking and current number of cigarettes per day, medication use, alcohol consumption, number of first degree and second degree relatives with an intracranial aneurysm (either unruptured or ruptured), and an EQ-5D-5L questionnaire is completed by the patient.
- Collection of aneurysm characteristics based on reviewing medical data: 1) number of intracranial aneurysms; 2) anatomical site(s) of the UIA; 3) maximum UIA diameter; and 4) aneurysm shape.
- A blood pressure will be measured in sitting position.
- If the time between screening visit and baseline visit exceeds so much time (depending on the cycle of the patient) that another pregnancy test is necessary, an additional rapid test will be performed.
- Clinical chemical parameter may be controlled, if the investigator decides they are necessary.
- A baseline assessment for symptoms of potential adverse effects of ASA is performed prior to beginning the therapy.
- Trial medication is provided to patients randomized to the intervention group.

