#### 9.4 Interim Analyses

The DSMB will review data of two interim analyses on the primary outcome to assess the strength of the efficacy data. The first interim analysis will be carried out after 235 patients have had their 3-year outcome assessment; the second one after 470 patients have these outcome data. The DSMB will also check the assumptions for sample size calculations. The DSMB can recommend the Steering Committee of the PROTECT-U trial to:

- Adjust the sample size
- Early terminate the study when there is clear and substantial evidence of benefit, based on a significant (with alpha 0.1%) reduction in aneurysm growth and rupture (according to the Peto approach of interim analysis with alpha 5% at final analysis); a different stopping rule may be suggested by the DSMB.
- Early terminate the study when there is evidence of severe harm based on SAE reporting, outcome, and case fatality
- Early terminate the study in case accrual rates are too low to provide adequate statistical power for identifying the primary endpoint
- The Steering Committee and the DSMB will agree on the approach to early termination (stopping rules) and the statistical methods used for efficacy evaluation beforehand. This approach will be described in a separate DSMB charter.

After the inclusion of 100, 300 and 600 patients, and if needed after later time points, the proportion of patients with aneurysms <3 mm will be analysed. Patients in this subgroup have the lowest risk of aneurysm growth and rupture. Care should be taken that the proportion of patients with aneurysms <3 mm does not exceed 30% of the total study cohort, so that the power calculation is not jeopardized. With 776 patients to be included, no more than 230 patients with aneurysms <3 mm should be included.

Because the first formal interim analysis will take place after 235 patients reached the 36 months visit, an additional two preliminary interim analyses will be done based on the first 235 and 470 patients, at the timepoint 12 months after randomization of subject 235 and 470 respectively, with all routinely obtained follow-up data available. To this end local reports on aneurysm growth will be used.

Interim analysis reports will be prepared and supported by a member of the data management team of the KKS and then forwarded to the DSMB. The results will not be disseminated inside or outside the study team.

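### Section 9.3 rests the primary comparison on the crude risk ratio and adds the covariate-adjusted one only as an extra, forgoing about 1 to 4 points of power under assumed prognostic strength

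*Protocol*

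**What the plan says.** Protocol 9.3 takes the primary effect as a risk ratio from a Poisson model, by intention to treat: "The precision of the RR estimates will be described with 95% confidence intervals obtained from the Poisson model". It continues: "In addition to crude analyses, we will do an analysis adjusted for the main risk factors of the primary outcome", and lists size, shape and location of the aneurysm, age and smoking. No sentence labels either result as the deciding one. The wording makes the crude comparison the base and the adjusted one an addition. Final details are left to the statistical analysis plan.

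Other sections bear on this:

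- **9.1** assumes "15% in the standard treatment group and 8.25% in the intensive treatment + ASA group" and concludes: "an alpha of 0.05 and a power of 80%, 353 patients are needed in each group".
- **9.4** tests "with alpha 5% at final analysis" after two interim looks. It also caps aneurysms under 3 mm at 30% of the cohort to protect the power assumption.
- **5.5.1** says: "Stratification will occur according to centre". None of the five factors is balanced by design.
- **6.2** provides for "Collection of aneurysm characteristics based on reviewing medical data", covering site, largest diameter and shape, and takes a smoking history. **10.1** adds date of birth.

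**The concern.** The protocol names the factors it regards as the chief determinants of the outcome, collects all of them before treatment starts, and then leaves them out of the comparison that decides the trial. The size cap in 9.4 shows that the authors consider aneurysm size prognostic enough to affect power.

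Under a log link the risk ratio is collapsible. With a common ratio across patients, the crude and adjusted models estimate the same quantity. If the ratio varies, a standardised risk ratio still targets the marginal effect. Adjustment therefore leaves the question unchanged and removes outcome variation that the crude test leaves in the standard error. What is at stake is some power, obtainable without enrolling anyone.

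**Working it through.** **1. The plan's own figure.** Inputs from 9.1: risks 0.15 and 0.0825 (ratio 0.55), alpha 0.05, power 80%. Two-sided testing is taken from the planned 95% interval. With pooled variance and mean risk 0.11625:

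n = [1.960 × √(2 × 0.11625 × 0.88375) + 0.8416 × √(0.15 × 0.85 + 0.0825 × 0.9175)]² / (0.15 − 0.0825)²

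= (0.8884 + 0.3794)² / 0.004556 = 352.8, so **353 per arm**.

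This matches 9.1 exactly, and power at 353 is 80.0%. The one-sided version gives 278. The calculation is unadjusted, so no covariate information enters the planned 80%. Expected events: 353 × (0.15 + 0.0825) = 82.

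**2. Analytic gain.** The protocol gives no AUC or R², so both are assumed ranges. If baseline factors explain a share R² of outcome variance, the effective size is 353/(1 − R²) per arm.

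| R² (assumed) | Power at 353 per arm | n per arm for 80% |
|---|---|---|
| 0.02 | 80.8% | 346 |
| 0.05 | 82.0% | 336 |
| 0.10 | 84.0% | 318 |
| 0.15 | 86.0% | 301 |
| 0.20 | 88.0% | 283 |

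These figures are optimistic if R² is read as the control-arm value. Under a constant ratio of 0.55, R² in the treated arm is only 0.55² × 0.1275/0.0757 = 0.51 times that in the control arm.

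**3. Simulation.** There were 353 per arm and 4,000 trials per setting. Five independent, normally distributed baseline covariates determined control risk (mean 15%), and the treatment ratio was 0.55. Crude and adjusted analyses used the same simulated data. The standard error of one power estimate is √(0.8 × 0.2/4000) = 0.6 point.

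| AUC (assumed) | Control-arm R² | Crude, robust | Adjusted Poisson, robust | Adjusted, standardised ratio | Gain (points) |
|---|---|---|---|---|---|
| 0.50 (no prognostic value) | 0 | 79.9% | 79.6% | 79.9% | −0.3 / 0.0 |
| 0.63 | 0.03 | 79.6% | 80.5% | 80.6% | 0.9 / 1.0 |
| 0.71 | 0.08 | 80.5% | 81.9% | 82.4% | 1.4 / 1.9 |
| 0.75 | 0.12 | 80.6% | 83.3% | 83.8% | 2.7 / 3.2 |
| 0.80 | 0.18 | 80.2% | 84.5% | 85.6% | 4.3 / 5.4 |

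Under no treatment effect, the adjusted analyses rejected in 4.8% to 5.4% of trials.

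**The case against.** The strongest reply is that nothing here is wrong. An unadjusted intention-to-treat risk ratio is a legitimate primary analysis, it agrees with the sample size formula, and statisticians reasonably differ on the choice. That stands, and it limits the point to an efficiency recommendation.

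The prognostic strength is also unquantified. The roughly thirty-fold spread in 5-year rupture risk in 1.1 covers unruptured aneurysms generally. By 1.3 and 3.1, this trial enrols mostly low-to-intermediate-risk patients, and its endpoint is driven mainly by growth. In the lower half of the assumed AUC range the gain is only about 1 to 1.5 points. The simulation also used continuous covariates, whereas location, shape and smoking are categorical. This stands too.

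Three stronger readings are tempting, and the protocol does not support them:

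- A reader might infer that the primary result has two competing readings at 5%, to be chosen after the data are seen. But 9.3 ranks the two by making the adjusted analysis an addition, and it requires the statistical analysis plan to be authorised before the database is opened.
- A reader might infer that the design has no way to recover power. But 9.4 has the DSMB check the sample size assumptions and lets it recommend a different sample size.
- A reader might infer that more baseline variables, such as hypertension or earlier haemorrhage, ought to be added. The protocol does not list them as adjustment factors, and the argument here does not need them.

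The unseen statistical analysis plan may also name the adjusted ratio as primary. The point therefore addresses the order that the protocol itself sets.

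**Conclusion.** The point holds as forgone efficiency. On its natural reading, 9.3 lets the crude ratio decide, and the five listed factors contribute nothing to that test. Making the adjusted ratio primary would add about 1 to 4 points of power at 353 per arm for an AUC between 0.63 and 0.80, and slightly more at the top of that range with a standardised ratio. Type I error stays near 5%, and there is essentially no loss if the factors turn out not to be prognostic.

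The size rests on an assumed AUC, the planned 15% and 8.25% risks, a constant risk ratio and robust variance. The direction rests only on the factors having some prognostic value, which the protocol asserts. The validity of the planned test is not in doubt.

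**What to change.** State in 9.3, and carry into the statistical analysis plan, that the primary test and 95% interval come from the risk-ratio model adjusted for the five factors already listed, as measured at baseline, and that the crude risk ratio is supportive. Specify robust variance or a standardised risk ratio. In the same simulations, model-based Poisson variance gave crude power of only 76% to 77%, which would outweigh much of the gain. Keep size continuous and use few categories for location, shape and smoking. The sample size does not change.

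Costs:

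- **Parameters.** If location and shape each take two groups, as in the subgroup definitions in 9.3, and smoking takes at most three, the model has up to seven parameters besides the intercept, including treatment. That is about 82/7 = 11.7 expected events each.
- **Several aneurysms.** A prespecified rule must say which aneurysm supplies size, shape and location in patients with more than one.
- **Interim looks.** The text should say whether the looks in 9.4 use the same model. With 235 patients assessed, only about 235 × 0.11625 = 27 events are expected, which is few for five factors.

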## 4.6 Criteria for Withdrawal

### 4.6.1 Withdrawal of Patients from Treatment

Any patient can withdraw from the treatment at any time without personal disadvantages and without having to give a reason. Patients who discontinue participation in the clinical study on their own or patients who are withdrawn by the investigator, for reasons other than disease progression (i.e. in case of AEs, protocol violations), will be defined as premature withdrawals. Withdrawn patients will be asked to attend a final follow-up visit and to return unused trial medication. Premature withdrawals will not be replaced. The time of treatment discontinuation must be documented in the patient file and on the CRF.

The investigator can also discontinue the participation of a patient in the study after considering the risk-to-benefit ratio, if he/she no longer considers the further treatment of the patient according to study protocol justifiable. The date of and the primary reason for the withdrawal, as well as the observations available at the time of withdrawal, are to be documented on the CRF. Reasons leading to the withdrawal of a patient can include the following (**one primary reason must be determined**):

- **Lack of efficacy** of the experimental intervention
- **Intolerable adverse events** from **both** components of the intervention (intensive blood pressure control **and** ASA-medication), e.g.
  - Any bleeding that results in hospital inpatient treatment
  - Severe skin reaction and/or asthma requiring treatment with medication exceeding a single dose
  - Gastric ulcer, if not possible to manage by gastroprotective co-medication
  - Severe orthostatic hypotension
- Disease progression
  - In patients with 1 intracranial aneurysm, end of treatment applies if aneurysm rupture (SAH) occurs or interventional treatment of the aneurysm (endovascular or neurosurgical). Patients who have multiple aneurysms can stay in the trial if growth, rupture or preventive treatment of 1 aneurysm occurs
- **Lack of patient's cooperation**, e.g.
  - Patient's request to withdraw
  - Lack of compliance, patient fails to attend the interim visits as agreed or perform self-medication according to schedule
- **Other reasons** (noting reason), e.g.
  - Other diagnosis than study disease
  - Did not meet major in-/exclusion criteria (coming to light after randomisation)

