## 6 DESCRIPTION OF TRIAL VISITS

The study period for an individual patient consists of a minimum treatment period of 36 months and a maximum treatment period of 120 months (all patients stay on intervention until 3 years of the last patients' enrolment, even if the primary endpoint has occurred for the purpose of the secondary endpoint analyses).

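### The ASA and blood-pressure component analyses in section 9.3 do not confine exposure to the time before the outcome, so they can show an effect, in either direction, where none exists

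*Protocol*

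**What the plan says.** Secondary objectives A and B (section 2.2) ask what ASA and intensive blood-pressure lowering each contribute. The two-arm design cannot separate them by randomisation, so section 9.3 plans non-randomised analyses with three exposure measures:

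- Blood-pressure therapy, where data from both arms can be used: "For this research aim we will relate the intensive blood pressure lowering therapy usage percentage to the primary outcome".
- Achieved pressure from the home device, intervention arm only: "For each patient we will calculate the percentage of time that systolic blood pressure is below 120 mm Hg".
- ASA, from tablet accountability: "For these analyses, we will use data on drug accountability (for acetylsalicylic acid use".

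The model given for the two component analyses is: "Analyses will be done with multivariable Poisson regression in which we will model cumulative incidence of the primary outcome at three years". The achieved-pressure analysis is described as similar. The only threat named is confounding, and the only safeguard is adjustment for other determinants of the outcome, including the other treatment component. No start, end or denominator is given for any of the three measures. Section 9.3 leaves final details to the statistical analysis plan, which was not available for this point.

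Three other sections bear on exposure after the outcome:

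- Section 4.6.1, for patients with one aneurysm: "end of treatment applies if aneurysm rupture (SAH) occurs or interventional treatment of the aneurysm". Patients with several aneurysms may stay in the trial.
- Section 1.1 says that substantial growth is what leads to repair.
- Section 6 says: "all patients stay on intervention until 3 years of the last patients' enrolment, even if the primary endpoint has occurred". It makes no exception for the one-aneurysm patients of section 4.6.1, so the two sections need to be reconciled. They are read together here.

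**The concern.** Each measure is one number per patient, entered as a fixed covariate against an outcome that occurs part-way through the period the number may cover. If the outcome ends treatment, the patient's usage falls because of the event, and the regression reads this as low usage preceding the event. If treatment carries on, or is tightened, after growth is seen, later exposure enters the summary and can push the estimate the other way. Adjusting for other determinants of the outcome does not remove this, because exposure altered by the outcome is not confounding by a baseline factor.

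These are the only analyses the protocol plans for objectives A and B. A spurious result for one component could not be checked against a randomised contrast within the trial.

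**Working it through.** **The plan's own figure.** The protocol gives no power or error rate for the component analyses. Its sample size (section 9.1) reproduces, so its inputs are usable. With p1 = 0.15, p2 = 0.0825, mean 0.11625, two-sided alpha 0.05 and power 0.80:

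n = [1.960·√(2·0.11625·0.88375) + 0.8416·√(0.15·0.85 + 0.0825·0.9175)]² / 0.0675² = (0.888 + 0.379)² / 0.004556 ≈ 353 per group.

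**Mechanism.** From the protocol: 353 intervention patients and 8.25% three-year risk, so 353 × 0.0825 = 29.1 events. Assumed: no treatment effect, event times uniform over months 6–36 (mean 21), adherence Beta(8, 1.5), and usage as a share of 36 months.

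- Mean adherence is 8/9.5 = 0.842. The SD is √[8·1.5/(9.5²·10.5)] = 0.113.
- An event patient who stops has expected usage 0.842 × 21/36 = 0.491, a shortfall of 0.351.
- If 10%, 25% or 50% of event patients stop, mean usage among event patients falls by 0.035, 0.088 or 0.175. That is 0.31, 0.78 or 1.56 SD, produced entirely by the event.

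**Null simulation** (same inputs, crude Poisson model with robust variance, two-sided 5% test). Ranges are the spread over separate runs.

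| Setting | 10% stop | 25% stop | 50% stop |
|---|---|---|---|
| Intervention arm, fixed 36 months: RR per 10 points (truth 1.0) | 0.82–0.85 | 0.71–0.72 | 0.63 |
| Same: false positives | 33–36% | 83–85% | 98–99% |
| Both arms, controls at zero usage: false positives | 5–8% | 10% | about 40% |
| On-treatment denominator, constant exposure: false positives | 4% | 7% | 6% |
| On-treatment denominator, 6-month build-up: false positives | 8–9% | 20–21% | 52–54% |

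With nobody stopping, the rate was 4% in one run and 7% in another of 300 trials, where the Monte Carlo standard error around 5% is √(0.05·0.95/300) = 1.3 points. The pooled RR per 10 points was 0.99, 0.98 and 0.96.

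**Second set of assumptions** (388 patients, section 4.1; 15% risk; event times uniform over 36 months; adherence Beta(4, 2); fixed 36 months). False protective findings, nominally 2.5%, were 26%, 68% and over 99% at 10%, 20% and 50% stopping in the intervention arm. With both arms they were 8%, 14% and 73%.

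**Direction.** In that second set, if nobody stops but exposure rises by 10 points after the event, the RR (100% versus 0% exposure) is 3.9, with 41% false harm. If 20% also stop, it is 0.54, with about 19% false protection. If the rise is 20 points and 20% stop, the two nearly cancel (RR 1.25, about 3% each way).

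**Is cutting the record at the event enough?** When exposure is averaged over observed time and every event patient's record ends at the event, constant exposure gives RR 1.05 and 2% false protection. With a 6-month linear build-up the same rule gives RR 0.05 and 99.8% false protection, because early events are averaged over the low start-up months. Truncation alone can therefore create the bias it is meant to remove.

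**The case against.** The strongest objection is that section 9.3 states no window or denominator, and that defining an exposure percentage is ordinary work for the statistical analysis plan. A reader might infer that the protocol prescribes exposure over the whole period. It does not say so, and an on-treatment denominator with constant exposure leaves essentially no bias. This stands as a limit on the size. It does not dispose of the point: the protocol has already chosen a fixed per-patient summary against three-year cumulative incidence, and a denominator definition alone does not repair that if exposure builds up.

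A reader might also infer that the outcome as such lowers exposure and that the result must be false protection. The documents do not support this:

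- Growth alone does not end treatment under section 4.6.1. Rupture is rare (section 3.1 puts the five-year risk usually below 3%), so most events will be growth, and section 1.1 ties repair to substantial growth, whereas the endpoint is an increase of 1 mm or more.
- Patients with several aneurysms can stay in the trial.
- Blood-pressure drugs are not trial medication and are prescribed by the general practitioner (section 5.1.1), so the end of trial treatment need not end them.
- Tightening control after growth reverses the bias.

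The large one-arm figures also cannot be carried over to the blood-pressure usage analysis, which can use both arms. The pooled figures are much smaller, though they come from a crude model. Section 9.3 adjusts for the other component, which largely identifies the arm, and that adjusted version was not simulated.

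Finally, these are secondary analyses that the protocol itself calls non-randomised.

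**Conclusion.** The point holds in this form: the stated method lets exposure that follows from the outcome enter the exposure summary, and confounder adjustment does not remove it. The estimate can then be biased with no true effect, in a direction that depends on whether events cut treatment short or lead to its intensification.

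The size is conditional. The share of event patients who stop, the denominator, the build-up of exposure and the event times are all assumed. Across those assumptions the false-positive rate runs from near nominal to almost certain. The problem is clearest for ASA accountability within the intervention arm. It is weaker for blood-pressure usage with both arms pooled. It is also weaker for time below 120 mmHg: if device readings stop with treatment, the percentage over measured time does not fall mechanically, and bias then needs build-up or later intensification.

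The intention-to-treat primary analysis is unaffected. The method should be corrected, but the point does not threaten the trial's main conclusion.

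**What to change.** In section 9.3, for all three measures, count exposure only from randomisation to the earliest of first imaging showing growth, rupture, repair, death or month 36. Then analyse it in one of two ways:

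- as a time-updated covariate; or
- by landmark, for example exposure in months 0–12 related to later events among patients event-free at 12 months.

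One of these is needed as well as the cut-off, because truncation alone fails when exposure builds up. A null run with a 12-month landmark gave an RR of 0.98 and 6% false positives.

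The cost is a short change of text and modest programming. Imaging dates, discontinuation times, tablet counts and device readings are already collected (sections 4.6.1, 5.4.2, 6.3 and 10.1).

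There are two drawbacks. A landmark drops early events: with event times uniform over months 6–36, a share of (12 − 6)/30 = 20% is lost, leaving about 23 of 29 events in the intervention arm and a standard error larger by about 1/√0.8 = 1.12. A time-updated covariate replaces the stated cumulative-incidence Poisson model for these secondary analyses.
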